4.4 INTERIM ANALYSES

No interim analyses are planned for this study.

Statistical Analysis Plan

5.0 SUBJECT ENROLLMENT AND DISPOSITION

Subject enrollment, inclusion in analysis populations, number of subjects discontinuing before study completion, termination status, and the reason for premature discontinuation will be summarized by sequence with frequencies and, where appropriate, percentages of enrolled subjects. Data will also be provided in an appendix listing by subject.

Statistical Analysis Plan

6.0 BASELINE EVALUATIONS

This section addresses data that were collected only at the screening visit.

6.1 DEMOGRAPHICS AND BASELINE CHARACTERISTICS

Demographic and baseline characteristic data will be collected and will include age (based on date of informed consent), sex, ethnic group, race, height, weight, and BMI. Age will be calculated as an integer in years (rounded down) as the difference between the subject's date of informed consent and the date of birth. All demographic and baseline characteristic data available from the eCRF will be summarized and listed.

6.2 MEDICAL HISTORY

All medical and surgical history data, as well as current medical conditions will be summarized by category of medical condition and listed.

6.3 TOBACCO/NICOTINE PRODUCT-USE HISTORY

Subjects will be required to report tobacco product and nicotine product-use histories to satisfy study inclusion and exclusion criteria. The following characteristics of the subject's usual brand will be documented: brand, brand style, and flavor. The number of uses per day (single number, not a range) will also be listed and summarized (pooled over all brands) (n, median, mean, standard deviation, CV% and range).

6.4 USE TEST-PRODUCTS AGAIN SCORES

“Use the Product Again” VAS raw scores which can range from 0 to 100 mm (measured from left to right on the VAS), will be included in subject listings, but no summary statistics will be computed from them. The raw scores will be converted to a binary, “unwilling” vs. “willing” to use, response as follows:

VAS < 50 mm ≈ unwilling to use again VAS \geq 50 mm ≈ willing to use again.

Statistical Analysis Plan

An additional 3-level ordinal response will be defined as follows:

VAS < 50 mm ≈ unwilling to use again VAS = 50 mm ≈ don't care

VAS > 50 mm ≈ willing to use again.

Summary statistics [n (%)] will be computed for each level of the binary and 3-level endpoint, by test-product and by sequence. Summary statistics (n, minimum, maximum, median, mean, and standard deviation) of raw VAS scores will be computed by test-product, sequence and by binary “willing to use” category.

6.5 CLINICAL LABORATORY PARAMETERS

Clinical chemistry, hematology, urinalysis, urine cotinine, and viral assay data will be collected from each subject at the screening visit; however, there are no planned follow-up clinical lab assessments. Screening lab data will be listed for all subjects with flags for abnormal values and will be summarized. Clinical laboratory parameters will be summarized by parameter within panels (clinical chemistry, hematology, urinalysis, etc.), per Section 4.1.

6.6 ELECTROCARDIOGRAM DATA

12-lead Electrocardiogram (ECGs) will be performed at visit 2. Each subject's ECG will be scored as “normal”, “not being clinically significantly abnormal, or “clinically significantly abnormal”. The QT interval, QTc, PR, QRS duration and heart rate also will be recorded.

If not supplied, QTcF will be derived using Fridericia's heart rate correction formula:

$$QTcF = QT / (RR)^{1/3} \quad \text{where RR} = 60/\text{HR} \text{ (if not provided)}$$

The average of the triplicate readings collected from each subject will be calculated for each ECG parameter. Summary statistics (n, mean, median, SD, min and max) will be calculated and tabulated for each ECG parameter and by sequence and test product.

Statistical Analysis Plan

7.0 EVALUATION OF RESPONSE PARAMETERS**7.1 ANALYSIS OF PRIMARY RESPONSE ENDPOINTS**

Sham and test product-derived sample amount of each analyte as well as sham-corrected amount (SCA) of each analyte will be summarized, by test product, per Section 4.1. Sham-corrected analyte amounts will be computed by subtracting corresponding sham response values from test product response values.

Mixed effects ANCOVA models will be fit to separately to the following sham-corrected amount of 7 analytes that will be measured in exhaled breath repeatedly in each subject over the 4 days of Visit 2:

1. Nicotine
2. Glycerin
3. Propylene glycol
4. Menthol
5. Formaldehyde
6. Acetaldehyde
7. Acrolein

The Minimum Detection Limit (MDL) of each analyte is provided in Table 4.

Table 4. Limits of Detection for Exhaled Breath Analytes

Analyte	Nominal MDL (μg)
Propylene glycol	5
Vegetable glycerin	5
Nicotine	0.5
Menthol	0.5
Formaldehyde	0.2
Acetaldehyde	0.2
Acrolein	0.2

Statistical Analysis Plan

Analyte concentrations that are below the Minimum Detection Limit (MDL) will be set to the MDL value for analyses.

Two types of sampling containers were used for collection of the analytes from each subject's exhaled breath (Table 5). Sampling container 1 with one tube and one pad was used for capturing nicotine, glycerin, propylene glycol, and menthol while Sampling container 2 with one tube and 2 pads was used for capturing formaldehyde, acetaldehyde, and acrolein. Exhaled breath samples were collected in 2 independent sampling sessions, separated by 45 minutes, within each period (Figure 1B). Sampling container 1 was used to trap exhaled breath in the first sampling session, while sampling container 2 was used in the second sampling session.

There are two subsamples (1 tube + 1 pad) of each analyte, in each sampling container 1 and three subsamples (1 tube + 2 pads) of each analyte in sampling container 2. Enthalpy Analytical Company will provide data sets with the tube and pad analyte amount from each of the two types of Sample container, for each subject. Pad and tube MDL values of the same analyte will be different from one another. For each sampler, the final amounts for a given analyte will be computed in one of three ways:

1. When both the amounts of analyte in pad(s) and tube are above MDL, the exhaled breath sample (EBS) value will be the sum of the pad and tube values
2. When the amounts of analyte in pad(s) and tube are both below MDL; EBS value will be the sum of the two MDL values. However, since the MDL is volume dependent, the sum will be considered as below MDL (i.e. <0.5).
3. When the amount of one analyte is MDL, but the other is above MDL. EBS will be the sum of the MDL value and the above BLLOQ value.

Descriptive statistics (number of observations, number of missing, mean, SD, median, minimum, maximum, the first quartile, the third quartile, 95% confidence interval, and coefficient of variation) will be tabulated for each of these analytes by test product. Frequency (n and %) of MDL values will be summarized for each product. If the percentage of MDL values for an analyte is more than 50% in any product group, the analyte will not be analyzed with a mixed model.

Statistical Analysis Plan

Each mixed model will be fit to the data by restricted maximum likelihoods. Covariance structures to account for dependencies among repeated measures, within subjects, will be selected for each model using AIC criteria.^[11] Four candidate covariance structures will be considered: compound symmetry, 1st order autoregressive, 1st order autoregressive with a random subject effect, and unstructured. Each model will include period-specific sham values (as a covariate), sequence, study product, and period as fixed effects; subjects nested within-sequence will be modeled as random effects. Standard residual analyses will be used to examine validity of assumptions for the fixed effect distributions. Response variables will be appropriately transformed (e.g., log, reciprocal, or square root) if the residuals indicate distributional assumptions don't hold. The models will be refit to the transformed data and residual analyses again be performed verify that the transformations corrected the problems.

Mean SCA response with (95% confidence limits), for each test product, will be estimated using SAS Least square means methods in each model. Estimates will be back-transformed to the original scale as necessary. Analyte LSmean estimates (with 95% CIs) for each test product will be tabulated for each model. As an example, the SAS Proc Mixed code to fit the Mixed effects ANCOVA model [with an AR(1) covariance structure] is provided below:

```
ods graphics on;
proc mixed data=evap_data method=REML;
  class seq test_product period subject;
  model Analyte = sham § seq period test_product/residual DDFM=KR;
  Random subject (seq); †
  Repeated /type=AR(1) subject=subject(seq); ‡
  lsmeans test_product/cl alpha=0.05;
  ods output lsmeans=mndat;
  title1 'Fit a 4x4 crossover design mixed effects ANCOVA';
  title2 'with a baseline(sham) covariate adjustment'; run;
```

§ amount (µg) of exhaled analyte from sham is entered in the model as a “baseline” covariate
† explicit inclusion of the subject in a random statement will depend upon the selected covariance structure (Little et al. 2000).
‡ AR1 requires a Random subjects statement, but the UN structure does not.

Statistical Analysis Plan

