4. In vivo mammalian genotoxicity test (MN assay; OECD474 and Comet assay; OECD489) (if needed).

The test products included in this study are outlined in [Table 2](#).

Table 2. Test Products Used in This Study

Non-menthol Test Products
Product A: Product XL25F = Test e-vapor product (currently marketed by Nu Mark LLC as MarkTen® XL Fusion [2.5% NBW]) [CVR2.6.8] Formula: 10321-75-1; Name: “Celine”; Label: 751.
Product B: Product XL40CB = Test e-vapor product (currently marketed by Nu Mark LLC as MarkTen® XL Bold Classic [4.0% NBW]) [CVR2.6.8] Formula: 10381-44-B; Name: “Rosetta”; Label: B44.
Menthol Test Products
Product C: Product XL35WM = Test e-vapor product (currently marketed by Nu Mark LLC as MarkTen® XL Winter Mint [3.5% NBW]) [CVR2.6.8] Formula: 10353-34-C; Name: “Monica”; Label: C34.
Product D: Product XL40MB = Test e-vapor product (currently marketed by Nu Mark LLC as MarkTen® XL Bold Menthol [4.0% NBW]) [CVR2.6.8] Formula: 10381-40-E; Name: “Spencer”; Label: 40E.

NBW = nicotine by weight.

A brief summary of in vitro assay results for the e-vapor formulas included in this study is provided below.

- Product XL35WM and Product XL40MB: These 3 formulations were negative in all 3 in vitro (Ames, NRU, and MN) assays.
- Product XL25F and Product XL40CB: Both formulations were negative in Ames and Neutral Red Uptake assays. In MN assay, Product XL25F formulation was positive and Product XL40CB formulation was equivocal (neither clearly positive nor negative as defined in the OECD487, i.e., inconclusive). While none of the e-liquid ingredients in the formulations are known mutagens or carcinogens, mixtures of e-liquid could potentially trigger genotoxic signals in cellular systems. For pharmaceutical drug candidates, OECD guidelines recommend in vivo genotoxicity assays to further investigate genotoxicity potential detected by an in vitro system (OECD474 and 489). Accordingly, ALCS is conducting in vivo genotoxicity testing of Product XL25F and Product XL40CB, using a conservative approach that evaluates two independent endpoints (in vivo MN and in vivo Comet responses) based on the combined OECD474 and 489. Preliminary results for Product XL25F are negative at both in vivo endpoints. Results for Product XL40CB are pending.

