3.0 ENDPOINTS AND COVARIATES

3.1 PRIMARY ENDPOINT

The primary endpoints for the study are each subject's sham-corrected amount of nicotine, glycerin, propylene glycol, menthol, formaldehyde, acetaldehyde and acrolein in exhaled breath from 10 puffs in each period for each of the 4 e-vapor products.

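### Non-detects in one product can remove the planned mixed model for every product: for menthol, A or B could cost C and D their adjusted estimates (minor, cheap to fix)

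*SAP*

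**What the plan says.** SAP 3.1 defines the primary endpoint, by subject and test product, as the "sham-corrected amount of nicotine, glycerin, propylene glycol, menthol, formaldehyde, acetaldehyde and acrolein in exhaled breath from 10 puffs in each period". SAP 7.1 plans a model for each analyte: "Mixed effects ANCOVA models will be fit to separately to the following sham-corrected amount of 7 analytes". The fixed effects are the sham covariate, sequence, product and period, and the output is an LS mean with 95% CI for each product.

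The same section then handles non-detects. It counts them by product ("Frequency (n and %) of MDL values will be summarized for each product") and adds the stopping rule: if the share is "more than 50% in any product group, the analyte will not be analyzed with a mixed model". No exception keeps the products with measurable values, and no other model is named. Descriptive statistics stay in any case, including a "95% confidence interval, and coefficient of variation) will be tabulated for each of these analytes by test product".

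Protocol 1.2.1, Table 2, lists A and B under "Non-menthol Test Products" and C and D as menthol products. SAP Table 4 gives a nominal menthol MDL of 0.5 µg.

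**The concern.** The rule has a sensible purpose. A product whose values are mostly set to the MDL tells a linear mixed model little. The unit it acts on is too wide, however. One product above 50% removes the model for all four, including products whose data are fully usable.

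For menthol this is foreseeable. If the non-menthol products yield mostly non-detects, the adjusted menthol estimates are lost for the two products in which menthol matters most, for a reason that lies in other products. The wording covers all seven analytes, but only for menthol do the documents give a reason to expect a split between products.

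At stake is a planned adjusted estimate for a primary analyte. SAP 4.2 also relies on the mixed model for missing primary data, and SAP 1.5 plans no imputation. If the model goes, that handling goes with it.

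**Working it through.** **Inputs.** 32 subjects in four sequences (SAP 1.5 and Table 2), each using all four products; the 50% rule applied by product (SAP 7.1). The plan's own figure reproduces: 32/4 = 8 replications of each sequence. Non-detect rates are my assumptions, because the documents give none.

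**Trigger.** 16/32 is exactly 50% and does not exceed it, so the rule needs at least 17 of 32. For one product the chance is P(X ≥ 17), with X binomial(32, p). For A or B at the same rate, taken as independent, it is 1 − (1 − P)².

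| Assumed rate p | One product | A or B |
|---|---|---|
| 0.3 | 0.5% | 1.0% |
| 0.4 | 9.2% | 17.5% |
| 0.5 | 43.0% | 67.5% |
| 0.6 | 83.5% | 97.3% |
| 0.7 | 98.6% | 99.98% |

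The same subjects use A and B, so positive correlation would lower the last column somewhat.

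**The wording is what decides.** If A and B were all non-detect and C and D all measurable, the pooled share would be 64/128 = 50.0%, which is not above 50%. Only the reference to any single product group removes C and D.

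**Can C and D be modelled alone?** Yes. That leaves 64 observations and 8 fixed-effect columns (sham covariate omitted), and the design has full rank, 8. With a random subject effect, complete data, and residual and between-subject variances of 1, the LS-mean SE is 0.250 in the C and D model and in the four-product model. The unadjusted mean has the same SE: √(2/32) = 0.250.

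**Cost of losing the model, complete data.** Each product occurs equally often in each period, so the point estimates stay the same, apart from the sham covariate. The raw CI widens only if there are period effects. A linear drift of d SD per period adds 1.25d² to the raw variance (1.25 is the variance of the period numbers 1 to 4):

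- d = 0.3: √(1 + 1.25 × 0.09) = 1.055
- d = 0.5: √(1 + 1.25 × 0.25) = 1.146

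A simulation of 4,000 runs (within-subject correlation 0.6, sham omitted) gave these mean 95% half-widths for C, raw against model:

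- no drift: 0.357 against 0.355 SD
- d = 0.3: 0.378 against 0.355 SD
- d = 0.5: 0.411 against 0.354 SD

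That is about 5 to 7% wider at 0.3 and 14 to 16% wider at 0.5, depending on the degrees of freedom used for the model. Losing the sham covariate multiplies the width by 1/√(1 − r²): 1.005, 1.048 and 1.155 for an assumed correlation r of 0.1, 0.3 and 0.5. There is no loss if the shams all sit at the MDL.

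**Cost with dropout.** At an assumed 5% dropout per period and drift of 0.3 SD per period, the raw mean is biased by about −0.02 SD and the model by 0.00.

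**Do sham samples count?** The rule does not say, and SAP 7.1 summarizes "Sham and test product-derived sample amount of each analyte" by test product. If they count, the trigger is 33 of 64. With every sham below the MDL and 5% of product-use samples below it, the rule fires in one product with chance 80.6%. With 80% of shams below the MDL, the chance is 1.7%.

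**Covariance candidates.** With C and D only, the sequences fill four of the six period pairs: (1,2), (1,3), (2,4) and (3,4). An unstructured matrix indexed by period is then not estimable. Every two-product subset has two distinct period lags, so AR(1) stays identifiable. With three products all six pairs occur.

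**The case against.** The strongest reply is that this is a clear, prespecified rule in a study sized for description (Protocol 9.1), and that declining a four-product model when one product is mostly substituted values is defensible. Counting by product and testing any product do not conflict, since the second needs the first. Every product keeps its mean, quartiles and 95% CI. The wider raw intervals need a drift of 0.3 to 0.5 SD per period, that is 0.9 to 1.5 SD from Day 1 to Day 4, which nothing in the documents supports. The raw interval is then conservative (96.2% coverage at 0.3). Missing data should also be limited: dropouts may be replaced, and subjects who do not tolerate a product leave before Day 1. Most of this stands, and it is why the point is minor. It does not justify withholding a model from products with usable data.

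The menthol trigger is an inference. Subjects try all four products on Day −1, and A or B follows a day of C or D in several sequences, so background menthol could lower the non-detect rate. That stands too.

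A reader might infer that the plan leaves open whether a sample with only the pad or only the tube below the MDL counts. SAP 7.1 largely settles it. Case 2, with both below, is labelled as below MDL. Case 3 ("When the amount of one analyte is MDL, but the other is above MDL") carries no such label and includes a quantified amount. On shams, the reference to a product group makes counting only product-use samples the more natural reading, and the high trigger rates above need nearly all shams below the MDL.

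**Conclusion.** The point holds as a cheap improvement of minor weight. As written, 17 of 32 product-use non-detects in one product remove the adjusted LS means and CIs for all four. For menthol this is likely if A and B have non-detect rates of about 50% or more, an assumption that rests only on the product classes.

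A reader might go further and infer that the menthol result for C and D is lost or biased. The documents do not support that: descriptive means and CIs stay, and with complete data the point estimates are the same apart from the sham adjustment. The loss is that adjustment, the period and sequence adjustment, precision if there are period effects, and the missing-data handling of SAP 4.2. Nor do the documents show that the rule will fire for menthol, or give a reason to expect it for another analyte.

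**What to change.** Replace the rule in SAP 7.1 with:

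> If more than 50% of the product-use samples (sham samples not counted; below MDL as in case 2) for an analyte are below MDL in a product group, that product is reported descriptively for that analyte and left out of its mixed model. The remaining products are modelled if at least two remain; otherwise all are reported descriptively.

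Keep the planned covariance candidates, with period as the repeated effect. The one exception is that a period-indexed unstructured matrix is not used when only two products remain. There is no reason to drop the AR(1) candidates.

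The cost is a few sentences and no extra data. The downside is that there is no modelled contrast with an excluded product (the plan does not tabulate such contrasts) and fewer observations for estimating the covariance.

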- Product B: Product XL40CB = Test EVP (currently marketed by Nu Mark LLC as MarkTen® XL Bold Classic [4.0% NBW]) [CVR2.6.8] Formula: 10381-44-B; Name: “Rosetta”; Cartridge Code: B44.
- Product C: Product XL35WM = Test EVP (currently marketed by Nu Mark LLC as MarkTen® XL Winter Mint [3.5% NBW]) [CVR2.6.8] Formula: 10353-34-C; Name: “Monica”; Cartridge Code: C34.
- Product D: Product XL40MB = Test EVP (currently marketed by Nu Mark LLC as MarkTen® XL Bold Menthol [4.0% NBW]) [CVR2.6.8] Formula: 10381-40-E; Name: “Spencer”; Cartridge Code: 40E.

SYNOPSIS (continued)

Study Objectives:

The primary objective of this study is to estimate the change in total amount of nicotine, glycerin, propylene glycol, menthol, formaldehyde, acetaldehyde, and acrolein levels in exhaled breath samples between sham (inactive battery and empty cartridge) and controlled test product use for four e-vapor products.

The secondary objectives of this study are:

- To estimate e-liquid use by changes in cartridge weight
 - Before and after controlled use in exhaled breath sessions
 - Before and after use during 12 hours of ad libitum use (per cartridge and in total over the 12 hours)
- To estimate puff count, average puff flow rate, average puff volume and average puff duration per cartridge and in total over the 12 hours during each 12 hours of ad libitum use
- To characterize responses to the Use Product Again Questionnaire after each 12 hour ad libitum use session

Study Design:

This is an open-label, 4-way crossover study designed to estimate the nicotine, glycerin, propylene glycol, menthol, formaldehyde, acetaldehyde, and acrolein levels in exhaled breath samples during use of four MarkTen® XL e-vapor products. The study will enroll approximately 32 adult e-vapor-using subjects. Each of the 32 subjects will provide two exhaled breath samples for all four test products. Subjects will make two visits to the site, one screening visit and one 4 day in-clinic visit to provide exhalation samples for four test products (one each day for 4 days). Subjects will also use their assigned test product ad libitum for 12 hours each day after the collection of exhaled breath samples. Subjects will be randomly assigned to a test product-use schedule at Visit 2, with one test product used per day.

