4.2 METHODS FOR HANDLING DROPOUTS AND MISSING DATA

The primary and some secondary responses will be analyzed in a mixed effects ANOVA/ANCOVA framework wherein subjects and dependencies among multiple measures of the same endpoint, taken from the same subject (one in each of 4 periods), will be modeled as random effects. One advantage of such models is that the model estimates will be unbiased as long as any data that may be missing, are missing at random (MAR).^[7, 8] This method of dealing with missing data has been demonstrated by Food and Drug Administration statisticians and others to be superior to LOCF.^[9, 10]

Missing safety and demographic data will not be imputed.

Statistical Analysis Plan

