7.2 ANALYSIS OF SECONDARY RESPONSE ENDPOINTS

Descriptive Statistics (n, mean, SD, Qtr1, median, Qtr3 and CV) will be provided, by product, for the following measurements:

- Exhaled breath sessions
 - Cartridge weight change by sampling session and overall
- 12 hour ad-libitum use session
 - Cartridge weight change by cartridge and overall (Template provided)
 - Total cartridge weight change (Template provided)
 - Number of cartridges used
 - Puff count by cartridge and overall
 - Total puff count
 - Average puff duration by cartridge and overall
 - Total puff duration by cartridge and overall
 - Average puff duration of the total puffs
 - Total puff duration
- Complete cartridge use over 12-hour ad-libitum use session
 - Puff count per complete cartridge (Template provided)
 - Average puff duration per complete cartridge
 - Total puff duration per complete cartridge
 - Cartridge weight change per complete cartridge

Definition of complete cartridge use: If a subject replaced a cartridge with a new cartridge, the previous cartridge is considered a complete cartridge. If subject only used one cartridge for the day, none would be counted as complete cartridge.

Mixed models will be applied to the following measurements:

- Total puff count over the 12-hour ad-libitum use session

Statistical Analysis Plan

- Total puff duration over the 12-hour ad-lib use session
- Average puff duration of the total puffs over the 12-hour ad-lib use session
- Total cartridge weight change over the 12-hour ad-lib use session
- Cartridge weight change calculated in each exhaled breath sampling session

Each model will include fixed effect terms for product, period and sequence. Subjects within sequence will be modeled as random effects. Models will be fit with SAS Proc Mixed, using the procedures described in Section 7.1.

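### No covariance structure on the SAP 7.1 list is specified to let variance differ by product, so the per-product 95% CIs are miscalibrated if product SDs differ

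*SAP*

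**What the plan says.** SAP 7.1 fits a separate REML mixed model to the sham-corrected amount (SCA) of each analyte, with the sham value, sequence, product and period as fixed effects. On the covariance it says: "Four candidate covariance structures will be considered: compound symmetry, 1st order autoregressive, 1st order autoregressive with a random subject effect, and unstructured". The structure "will be selected for each model using AIC criteria".

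SAP 4.2 describes the repeated measures as "taken from the same subject (one in each of 4 periods), will be modeled as random effects". The example code in SAP 7.1 has "Repeated /type=AR(1) subject=subject(seq", with no repeated effect before the slash and no grouping option. The per-product estimates and intervals come from "lsmeans test_product/cl alpha=0.05". Protocol 9.5.2 specifies only a random subject effect.

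Three other provisions of SAP 7.1 bear on the point:
- Residuals are checked. If they look wrong, the response is transformed, the model refitted and the estimates back-transformed.
- A descriptive 95% CI is tabulated by product, outside the model.
- An analyte is left out of the mixed model if more than 50% of its values are MDL values in any product group.

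SAP 7.2 carries the approach over to the secondary endpoints: "Models will be fit with SAS Proc Mixed, using the procedures described in Section 7.1".

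**The concern.** The primary objective asks for an estimate for each of four products, not for a contrast between them. Each interval should therefore reflect the spread of its own product. A model that pools the variance gives all four products the same standard error, whatever their individual spreads.

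Equal spread cannot be taken for granted for every analyte. Protocol Table 2 gives nicotine contents of 2.5, 4.0, 3.5 and 4.0% for A, B, C and D, and spread in micrograms may rise with the amount delivered. AIC cannot correct this, because it can choose only among the listed structures.

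At stake is the stated precision of the primary estimates. The study data are meant to support modelling of non-user exposure (Protocol 1.3; SAP 1.2). The point estimates are not said to be biased.

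**Working it through.** **1. The plan's own figure.** SAP 1.5 and Table 2: 4 sequences × 8 subjects = 32, which reproduces the stated sample size. Each product occurs 8 times in each period, and each product mean rests on 32 observations, one per subject. SAP 1.5 assumes no dropout.

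**2. What each candidate allows.**
- Compound symmetry, AR(1), and AR(1) with a random subject: one variance for every observation.
- Unstructured by period: four variances, belonging to periods. Each period contains the four products equally often, so each period variance is the same mixture of the four product variances.

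**3. Why unstructured by period does not help.** Relabel A→B, B→C, C→D, D→A. Sequence ABDC becomes BCAD, BCAD becomes CDBA, CDBA becomes DACB, and DACB becomes ABDC. The relabelling only permutes the sequences, so the design is unchanged. For any covariance matrix indexed by period, the four product LS means therefore have the same model standard error, apart from small differences through the sham covariate.

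**4. Closed form (balanced, complete data).**

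True SE for product k = SD_k/√32. Model SE = √(mean of the four product variances)/√32.

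Width ratio r_k = √(mean variance)/SD_k. Coverage = 2Φ(1.96 r_k) − 1.

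The documents give no product SD, so these SD ratios are assumptions:

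| SDs A:B:C:D | Mean variance | Width ratio | Coverage, % |
|---|---|---|---|
| 1:1:1:1 | 1 | 1 for all | 95 for all |
| 2.5:4:3.5:4 | (6.25+16+12.25+16)/4 = 12.625 | 1.42/0.89/1.02/0.89 | 99.5/91.8/95.3/91.8 |
| 1:1:1:1.5 | (1+1+1+2.25)/4 = 1.3125 | 1.15/1.15/1.15/0.76 | 97.5/97.5/97.5/86.6 |
| 0.5:1:1:2 | (0.25+1+1+4)/4 = 1.5625 | 2.50/1.25/1.25/0.625 | 100/98.6/98.6/77.9 |

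The second row assumes an equal coefficient of variation, with SD proportional to nicotine content.

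**5. Simulation.** There were 500 trials per scenario with the four stated sequences, 32 subjects, REML, the SAP's fixed effects including sham, and within-subject correlation 0.5. Intervals used t with 28 df in place of Kenward-Roger. Monte Carlo SE near 95% is √(0.95×0.05/500) ≈ 1 percentage point.

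| SDs A:B:C:D | AIC choice from the four | Unstructured by period | Unstructured by product | Descriptive CI |
|---|---|---|---|---|
| 1:1:1:1 | 96.2/94.6/96.4/95.2 | 96.2/93.6/95.4/94.8 | 95.8/94.2/95.4/94.8 | 96.2/94.0/96.0/95.0 |
| 2.5:4:3.5:4 | 99.6/92.0/96.4/92.0 | 99.2/91.0/95.4/92.0 | 95.0/94.2/95.4/95.2 | 95.0/94.4/96.0/95.4 |
| 0.5:1:1:2 | 100/98.2/97.4/78.2 | 100/97.4/96.8/75.6 | 95.8/95.0/94.2/95.4 | 96.2/95.0/93.8/94.8 |

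Entries are coverage in % for A/B/C/D. With SDs 2.5:4:3.5:4 (scaled so that C has SD 1), the AIC choice gave a mean CI width of 0.731 for every product. Product-specific variances gave 0.51/0.82/0.73/0.82.

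**The case against.** The strongest case on the other side has six parts.

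**Unequal spread is not shown.** Neither document gives a product SD, and Protocol 9.1 says that data are limited. With equal SDs nothing is wrong. This stands, so the point is conditional.

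**The reason for suspecting unequal spread is narrow.** Nicotine content bears on nicotine. It says nothing about glycerin, propylene glycol, the aldehydes, puff measures or cartridge weights. This stands; for those endpoints the documents give no particular reason, only no check.

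**Unstructured does free variances.** This is correct. Because the code names no repeated effect, row order sets the index, and data sorted by product would make the structure product-specific. But SAP 4.2 points to period, and AR(1) needs time order. An interval that depends on sort order is itself a reason to name the effect.

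**Transformation may cure it.** A constant-CV pattern, as in the nicotine illustration, has equal variance on the log scale, and SAP 7.1 provides for refitting and back-transformation. This stands in part. Unequal variance by product is not named as a trigger. The SCA is a difference that can be zero or negative, for example when product and sham are both non-detects set to the MDL, and then a log fails. A back-transformed log mean is also not the arithmetic mean amount.

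**Unpooled intervals are already planned.** The descriptive CIs held 93.8–96.2% coverage in both unequal-SD scenarios. This is a real partial safeguard, but the model LS means are also reported with CIs, and the SAP does not say which governs.

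**Menthol.** A reader might infer an extreme failure for menthol, with almost no spread in the two non-menthol products. The documents do not support that: if those products are mostly below the MDL, the 50% rule removes menthol from the mixed model.

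**Conclusion.** The concern holds in conditional form. No listed structure is specified to let variance differ by product, and with complete data the period-indexed candidates give all four product LS means the same standard error. If product SDs differ on the analysed scale, the model-based CIs err in a known direction: too wide for the less variable products, too narrow for the more variable.

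Over the range tried, coverage for the most variable product runs from 95% (equal SDs) through about 92% and 87% to about 78%. These figures rest on assumed SD ratios, balanced data and an analysis on the untransformed scale.

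Two stronger readings are tempting. One is that the intervals are wrong as planned; the documents cannot show this without product SDs. The other is that all four structures impose one variance; unstructured does not, since it frees variance by period or by whatever the row order implies. Nor do the documents say that these CIs themselves enter the exposure model, only that the study data do. This is a worthwhile, inexpensive improvement to the primary analysis, not a flaw in the design.

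**What to change.** In SAP 7.1, and through it 7.2:

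- Name the repeated effect explicitly in every REPEATED statement, so that the result does not depend on row order.
- Add product-heterogeneous candidates to the AIC list: `repeated test_product / type=CSH subject=subject(seq)`, or `type=UN` indexed by product, each without the separate random subject term. A random subject with an independent residual and `group=test_product` is another option. Do not combine AR(1) with `group=test_product`: each subject has one observation per product, so the correlation within a group cannot be estimated.
- Add a check of residual variance by product to the residual analyses.
- Take the LS-mean CIs from a product-heterogeneous structure when that check or AIC shows unequal variances.

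The cost is a few lines of text and code and some extra variance parameters. CSH has three more than compound symmetry (four variances and one correlation, against one of each); unstructured has more. If the variances are in fact equal, the CIs become slightly wider. The sample size of 32 is unaffected.
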